## **4. Primary Aim and Hypothesis**

### **Primary Aim**

To determine whether direct bypass surgery guided by multimodal neuronavigation is superior to empirical direct bypass procedure alone for preventing the primary endpoint (All strokes & death within 30 days post-surgery and ipsilateral hemorrhage afterwards) after cerebral revascularization surgery in ischemic MMD patients.

\*patients with TIA, stroke or other ischemic symptoms prior to enrollment that is attributed to progressive stenosis or occlusion in the terminal portion of the internal carotid artery and/or the initial portion of the anterior or middle cerebral arteries unilaterally or bilaterally and formation of abnormal collateral networks (moyamoya vessels) at the base of the brain.

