### **Primary Hypothesis**

As compared with empirical direct bypass procedure alone, direct bypass surgery guided by multimodal neuronavigation will decrease the risk of the primary endpoint over 12 months in patients with MMD.

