## **6. Study Endpoints**

### **6.1. Primary Endpoint**

All strokes & death within 30 days post-surgery and ipsilateral hemorrhage afterwards

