### **21.3. Statistical Analyses**

All analyses will be based on the intent-to-treat principle using the FAS, including only events adjudicated by the Clinical Events Adjudication Committee (CEC). The primary hypothesis will be tested using a Cox proportional hazards model with a factor for the treatment group. The time to the first event was used in the model when there were multiple events of the same type. P values and Confidence Intervals (CI) for the Hazard Ratio will be obtained according to the Wald statistic. The following statistics, in addition to HR with CI will be also presented in the summary tables of these analyses: the number of patients with event and Kaplan-Meier estimates of the event rate per treatment group calculated at EoT. Kaplan-Meier estimates of the cumulative proportion of patients with primary endpoint events will be calculated and plotted.

The potential impact of loss to follow-up will be evaluated by the sensitivity analysis.

A Cox proportional hazards model will be used to assess differences between study groups in the rate of primary endpoint under the following three scenarios: (1) all patients will be thought to experience primary endpoint event when the final disposition for the event adjudication is not determined. (2) only patients in the empirical bypass arm will be thought to experience primary endpoint event when the final disposition for the event adjudication is not determined. (3) only patients in the multimodal neuronavigation guiding bypass arm will be thought to experience primary endpoint event when the final disposition for the event adjudication is not determined. These results under the three scenarios will be compared with the result under the scenario in which all patients will be not thought to have primary endpoint event when the final disposition for the event adjudication is not determined. However, the primary analysis result will be reported in patients who are censored not to have the event occurrence when the final disposition for the event adjudication is not determined.

The analysis of and the secondary efficacy variable for the test of multimodal neuronavigation guiding bypass against empirical bypass will comprise the confirmatory analysis. No multiplicity adjustment will be made in all analysis including a confirmatory testing (subgroup analysis).

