## 21.7. Interim analyses

One interim analysis will be planned and conducted by the Data Monitoring Committee following the accrual and confirmation by adjudication of 50% of planned primary events. The stopping rule of Lan-DeMets approach to O'Brien-Fleming will be adopted for stopping for efficacy or futility. The efficacy stopping boundary at the interim analysis is a 2-sided p-value <0.0015 for the primary endpoint (one-year stroke or death). The final last level of significance with one interim analysis will therefore be 0.0489, with the family wise error rate controlled at 5.00%. The trial would be halted due to futility if nominal critical point (Standardized Z scale) for the primary endpoint crosses the internal boundary for futility ( $\pm 0.595$ ). It will be determined by the executive committee that the trial will be continued or stopped due to the overwhelming efficacy or futility after recommendation of Data Safety Monitoring Board.

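### The interim analysis section gives the primary endpoint as stroke or death at one year, which is not the primary endpoint defined in the synopsis, Section 4 and Section 6.1

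*Protocol*

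**What the plan says.** Section 6.1 defines the primary endpoint as "All strokes & death within 30 days post-surgery and ipsilateral hemorrhage afterwards". The synopsis uses the same words, and so does the Primary Aim in Section 4: "for preventing the primary endpoint (All strokes & death within 30 days post-surgery and ipsilateral hemorrhage afterwards"). The Primary Hypothesis adds the horizon, namely that the guided procedure "will decrease the risk of the primary endpoint over 12 months in patients with MMD". Section 21.3 gives the final test: "The primary hypothesis will be tested using a Cox proportional hazards model with a factor for the treatment group".

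Section 21.7 plans one interim look, "following the accrual and confirmation by adjudication of 50% of planned primary events". Its efficacy boundary is a two-sided p-value below 0.0015 "for the primary endpoint (one-year stroke or death"). The final level is 0.0489, "with the family wise error rate controlled at 5.00"%. The futility sentence in the same paragraph ("The trial would be halted due to futility if nominal critical point" and so on) refers to the primary endpoint without describing it.

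Section 17 describes the primary endpoint in a third way, as a stroke in the territory of the operated side.

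**The concern.** The definition in Section 6.1 narrows after day 30. Up to then any stroke and any death count; afterwards only hemorrhage on the operated side does. The gloss in Section 21.7 has no such narrowing, so it keeps counting every stroke and every death for a year. The year itself agrees with the Primary Hypothesis. The conflict lies in which events count.

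The paragraph with the gloss governs whether the trial stops early. A monitoring board that follows it literally would compare the arms on late ischemic strokes and late deaths, which the final Cox model of the Section 6.1 endpoint leaves out. The event trigger and the futility rule have no definition of their own there, and the only description of the endpoint in that paragraph is the conflicting one. The stated 50% information fraction and the alpha statement both presuppose one endpoint at both looks.

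The gloss also cuts across the endpoint hierarchy. Section 6.2 lists contralateral infarction within 1 year as a secondary endpoint. Under Section 21.7 a symptomatic contralateral infarction at month 6 would be a primary event.

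There is a smaller link to follow-up. Section 16 follows patients until the primary endpoint or the end of the trial, so the definition bears on when follow-up may end, although the same section promises best-effort collection of endpoint information.

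**Working it through.** **1. The two definitions side by side.** Stroke types are taken from the appendix, Definition of End Points.

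| Event | Section 6.1 | Section 21.7 |
|---|---|---|
| Any stroke or death, to day 30 after surgery | counts | counts |
| Ischemic stroke, either side, day 31 to one year | no | counts |
| Contralateral hemorrhagic stroke, day 31 to one year | no | counts |
| Death not preceded by a Section 6.1 event, day 31 to one year | no | counts |
| Symptomatic ipsilateral hemorrhagic stroke, day 31 to one year | counts | counts |
| Asymptomatic ipsilateral hemorrhage, day 31 to one year | counts if read literally | no |

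The last row follows from the appendix, which requires neurological symptoms for a hemorrhagic stroke and lists asymptomatic hemorrhage separately. Section 6.1 says hemorrhage and does not mention symptoms. The disagreement therefore runs in both directions, although this row depends on a literal reading.

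**2. Duration of the disagreement.** With 30 days per month (Section 16) and surgery taken to fall on day 0, the definitions differ over (360 − 30)/360 = 0.917 of the period, or 11 of 12 months. This measures time and not events.

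**3. The plan's own boundaries.** The Lan-DeMets O'Brien-Fleming-type function at one-sided 0.025 and information fraction t = 0.5 spends 2[1 − Φ(z₀.₉₈₇₅/√0.5)] = 0.00153. This gives z = 2.963, or two-sided p = 0.00305, and a final two-sided level of 0.0490. The stated final level of 0.0489 is close to this. The stated 0.0015 matches only as a one-sided value, although it is labelled two-sided; that is a separate matter. The rest of the check uses the boundaries as printed.

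**4. Effect on type I error.** Two-sided 0.0015 gives |Z₁| > 3.175, and two-sided 0.0489 gives |Z₂| > 1.969. Under the null, with (Z₁, Z₂) bivariate normal, P(|Z₁| > 3.175 or |Z₂| > 1.969) is:

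- same endpoint at both looks, correlation √0.5 = 0.707: **0.0493**
- unrelated endpoints, correlation 0: 1 − (1 − 0.0015)(1 − 0.0489) = **0.0503**
- upper bound for any correlation: 0.0015 + 0.0489 = **0.0504**

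Using different endpoints at the two looks hardly moves the error rate. The harm is a stop-or-continue decision made on the wrong events.

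**5. Number of discordant events.** This cannot be derived. Section 21.1 gives no sample size calculation, Section 21.7 gives no planned number of events, and the Study Rationale gives no late rates by type and side.

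**The case against.** The strongest reply is that this is one mistaken parenthesis. Its operative words are still the primary endpoint, a term defined identically three times elsewhere. The trigger and futility sentences carry no gloss and would take that definition by default. This is a reasonable way to read the paragraph, but the protocol does not say so, and a reader of Section 21.7 alone finds only the conflicting description.

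A second reply is that the efficacy boundary is hard to reach. As an assumption, take the 15% ceiling on perioperative stroke or death in Section 15 as the event rate. Then 100 patients give 15 events, and half of that is 7 to 8 at the interim. If all 8 fell in one arm, the log-rank Z would be about 2.94 with 50 per arm at risk, or 3.06 with 25 per arm, both below 3.175. About 9 to 10 events, all in one arm, would be needed. This shows that an efficacy stop is unlikely at that rate, but the rate is assumed, and the wider event set of Section 21.7 would yield more events. A stop also needs a board recommendation and an executive committee decision, but both would be looking at the endpoint named in Section 21.7.

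A third reply is that 11 of 12 months overstates the matter, because risk is concentrated early. This stands. The Study Rationale gives about 4% per hemisphere in the first 30 days and then 96% stroke-free over 5 years. Spread evenly, that is 4 × 11/60 ≈ 0.7 late strokes per 100 over 11 months. The other cited figure, 10.1% at 2 years, gives (10.1 − 4) × 11/23 ≈ 3 per 100. The sources differ in population and in unit (hemisphere or patient), and neither separates type or side, so this is only a rough range for all late strokes. It suggests few discordant events, though at 50 per arm a few can matter.

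**Conclusion.** The concern holds. The protocol gives two incompatible descriptions of its primary endpoint, and the one in Section 21.7 is attached to the rule for stopping early. This is an error in the text as it stands, and not a detail left to the statistical analysis plan.

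It should be fixed, but it does not threaten the error rate: overall two-sided alpha stays between about 0.0493 and 0.0504 in the cases checked. The number of events affected is unknown and probably small if the rates in the Study Rationale apply. What is at stake is whether the interim decision and the final test concern the same question. The conclusion rests on the wording alone; the alpha figures assume the printed boundaries and a look at 50% information.

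**What to change.** In Section 21.7, replace the parenthesis after the words primary endpoint with the Section 6.1 definition. Add one sentence stating that this single definition applies to the 50% event trigger, the efficacy and futility tests, the final Cox model and the sensitivity analyses in Section 21.3. Reconcile the Section 17 wording of the primary endpoint with Section 6.1; no change to clinical management is proposed.

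The p-value boundaries do not change, because they depend only on alpha and the information fraction. The cost is a wording amendment submitted to the IRB under Sections 24 and 25, with no change to data collection, sample size or the final analysis. The correction does not supply the missing planned event number, so the 50% trigger still needs that figure before it can be used.

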## 21.8. Censoring

Patients who have not had the event(s) in question will be censored at the earliest of EoT visit and the last study contact when all components of the endpoint in question were assessed. Lost patients in whom we cannot accurately determine if the primary endpoint occurred will be censored at the last contact date at which the patient was known to be free from a primary endpoint.

If the study is stopped early at the interim analysis, the mentioned-above censoring rule will apply. When the trial is determined to be stopped, all patients who have not completed the treatment period will be required for a EoT visit as soon as possible.

## 22. Data Safety Monitoring Committee

A Data Safety Monitoring Board (DSMB) is composed of Academic Members, including an independent statistician, who are not otherwise participating in the trial. A DSMB charter including membership role and responsibilities will be approved by both the DSMB and the Executive Committee before the start of the trial. DSMB will meet approximately every three months to review the progress of this study (e.g enrollment, site performance, meeting risk factor targets) as well as data on the safety of both

treatment arms (e.g., complications of multimodal neuronavigation guiding precise bypass surgery) to ensure that the study meets the highest standards of ethics and patient safety. Using guidelines established by the committee and the principal investigators before the study begins, the DSMB may recommend termination of the study if one treatment arm is found to be unequivocally more efficacious than the other or if one of the treatment arms is found to be unsafe. Additionally, the DSMB may recommend modifications to the protocol if a reversible safety issue is identified. A letter including written recommendations and their rationale will be provided to the Chairs of the Steering Committee immediately after each DSMB meeting. This letter will be provided to the central IRBs at their request.

Committee member: ky-2018-3-16

### **23. Study Drug Supply and Accountability**

The study product including aspirin will be purchased by study patients. All study drug supplies in the study will be stored in a secure, safe place, under the responsibility of the Investigator or other authorized individual, and under the conditions described on the labeling.

The Investigator, the Hospital Pharmacist, or other personnel allowed to store and dispense Investigational Product will be responsible for ensuring that the Investigational Product used in the clinical trial is securely maintained as specified by the Sponsor and in accordance with the applicable regulatory requirements.

All Investigational Product shall be dispensed in accordance with the Investigator's prescription, and it is the Investigator's responsibility to ensure that an accurate record of Investigational Product issued and returned is maintained.

Any quality issue noticed with the receipt or use of an Investigational Product (labeling, expiry date, etc.) should be promptly reported to the Sponsor, who will initiate a complaint procedure.

Under no circumstances will the Investigator supply study Product to a third party, allow the study Product to be used other than as directed by this Clinical Trial Protocol, or dispose of study Product in any other manner.

### **24. Regulatory Requirements**

The study will be conducted in accordance with the China Food and Drug

Administration (CFDA) and Good Clinical Practice.

Each investigator will sign an Investigator Agreement. Protocol amendments are not allowed by any investigator without prior approval from the Sponsor-Investigator. All changes to the protocol should be submitted to the site's IRB for review and approval as appropriate.

## **25. Institutional Review Board/Independent Ethics Committee(IRB/IEC)**

The Investigator or the Sponsor must submit this Clinical Trial Protocol to the central IRB located at Peking University International Hospital, and is required to forward to the Sponsor a copy of the written and dated approval/favorable opinion signed by the Chairman with Ethics Committee (IRB/IEC) composition.

The following information should be clearly stated on the written approval/favorable opinion: the Clinical Trial information (study number, Clinical Trial Protocol title and version number), the documents reviewed (Protocol, Informed Consent Form, Investigator's Brochure, etc.), the list of voting members along with their qualification and the date of the review.

Investigational Product will not be released at the study site and the Clinical Trial will not be initiated until a copy of this written and dated approval/favorable opinion has been received by the Sponsor.

During the Clinical Trial, any amendment or modification to the Clinical Trial Protocol should be submitted to the Ethics Committee (IRB/IEC). It should also be informed of any event likely to affect the safety of patients or the continued conduct of the Clinical Trial, in particular any change in safety. All updates to the Investigator's Brochure will be sent to the Ethics Committee (IRB/IEC).

If requested, a progress report will be sent to the Ethics Committee (IRB/IEC) annually and a summary of the Clinical Trial's outcome at the end of the Clinical Trial.

[figure not shown]

## APPENDIXS

### Study Design Chart

**Study Flow Chart**

**Schedule of Visits and Tests**

	Visit 1	Visit 2	Visit 3	Visit 4	Visit 5	Visits after 1 year	Event visit
Assessments	Screening/Randomize	At discharge	At Day 90 ±7d	At Day 6 months ±14	At 1 year ± 1 month	Every 12 months ±1 month	
Informed Consent	X						
Eligibility criteria	X						
Patient Randomization	X						
Relevant medical history	X						
Demographics	X						
MRI	X						
CTP	X						
DSA before Surgery							
Vital signs	X						X
Modified Rankin Score	X	X	X	X	X	X	X
NIHSS	X	X	X	X	X		X
Modified Barthel Score	X	X	X	X	X		X
Process Core Labs	X						
MRI after surgery		X	X	X	X		
CTP after surgery		X	X	X	X		X
DSA after surgery		X	X	X			X
Compliance reminder			X	X	X	X	X
Current Medications	X	X	X	X	X	X	X
Risk factor Management	X		X	X	X	X	X
AEs, SAEs and Endpoints		X	X	X	X	X	X

**Definition of End Points**

Stroke	Sudden symptoms and signs of focal disturbance of cerebral function associated with cerebral circulation disorders..
Ischemic stroke	An acute focal infarction of the brain or retina. Criteria: (1) acute onset of a new focal neurological deficit with clinical or imaging evidence of infarction lasting more than 24 hours and not attributable to a non-ischemic etiology (not associated with brain infection, trauma, tumor, seizure, severe metabolic disease, or degenerative neurological disease); or (2) acute onset of a new focal neurological deficit and not attributable to a non-ischemic etiology lasting less than 24 hours, but accompanied by neuroimaging evidence of new brain infarction; or, (3) rapid worsening of an existing focal neurological deficit lasting more than 24 hours and not attributable to a non-ischemic etiology, and accompanied by new ischemic changes on brain MRI or CT, and clearly distinct from the index ischemic event.
Hemorrhagic stroke	An acute extravasation of blood into the brain parenchyma or subarachnoid space with associated neurological symptoms.
TIA	A neurological deficit of sudden onset, resolving

	
completely, attributed to focal brain or retinal ischemia without evidence of associated acute focal infarction of the brain. Criteria: rapid onset of a focal neurological deficit that is without evidence of acute focal infarction of the brain, and is not attributable to a non-ischemic etiology (brain infection, trauma, tumor, seizure, severe metabolic disease, or degenerative neurological disease)

Symptomatic intracerebral hemorrhage
	
Any extravascular blood in the brain associated with clinical deterioration, as defined by an increase of 4 points or more in the score on the NIHSS, or that led to death and that was identified as the predominant cause of the neurologic deterioration. Intracerebral hemorrhage is defined as an acute extravasation of blood into the brain parenchyma. Criteria: evidence of hemorrhage in the brain parenchyma demonstrated by head imaging, surgery, or autopsy

Asymptomatic intracerebral hemorrhage
	
an acute extravasation of blood into the brain parenchyma without clinical deterioration. Criteria: evidence of hemorrhage in the brain parenchyma demonstrated by head imaging, surgery or autopsy


Other symptomatic intracranial hemorrhage
	
Any extravascular blood within the cranium associated with clinical deterioration, as defined by an increase of 4 points or more in the score on the NIHSS, or that led to death and that was identified as the predominant cause of the neurologic

	deterioration. Other Intracranial Hemorrhage is defined as an acute extravasation of blood into the subarachnoid space, epidural space, or subdural space with associated symptoms. Criteria: evidence of hemorrhage in the subarachnoid space, epidural space, or subdural space demonstrated by head imaging, surgery, or autopsy
Other Asymptomatic intracranial hemorrhage	An acute extravasation of blood into the subarachnoid space, epidural space, or subdural space without associated symptoms. Criteria: evidence of hemorrhage in the subarachnoid space, epidural space, or subdural space demonstrated by head imaging, surgery, or autopsy
Ischemic vascular death	Death due to ischemic stroke, myocardial infarction, sudden cardiac death, arrhythmia, pulmonary embolism, bowel or limb infarction, or any death not readily attributable to a non-ischemic cause
Hemorrhagic Vascular death	Death due to intracranial or systemic hemorrhage

**modified Barthel Scale**

	Independent	Need some help	Need more help	Totally dependent
Feeding	10	5	0	
Bathing	5	0		
Grooming	5	0	-	-
Dressing	10	5	0	-
Bowel control	10	5	0	-
Bladder control	10	5	0	-
Toileting	10	5	0	-
Chair transfer	15	10	5	0
Ambulation	15	10	5	0
Stair climbing	10	5	0	-
Items are rated based on the amount of assistance required to complete each activity Score _____				

**modified Rankin Scale**

The modified Rankin Scale (mRS) is a scale commonly used for measuring the degree of disability or dependence in the daily activities of individuals who have suffered a stroke, and it has become the most widely used clinical outcome measure for stroke clinical trials.

Description	Score (select one)
No symptoms at all	0 
No significant disability despite symptoms; able to carry out all usual duties and activities	1 
Slight disability; unable to carry out all previous activities, but able to look after own affairs without assistance	2 
Moderate disability; requiring some help, but able to walk without assistance	3 
Moderately severe disability; unable to walk without assistance and unable to attend to own bodily needs without assistance	4 
Severe disability; bedridden, incontinent and requiring constant nursing care and attention	5 

